STUDY PROTOCOL

Study name	Understanding Non-Response in Spine Fusion Surgery
Principal investigator	[name], MPH
Project lead	[name], MPH
Document Date	2/6/2019

CONTENTS

Study protocol	1
Abstract.....	2
Objective	2
Design.....	2
Recruitment Workflow Notes	2
Original Recruitment Design	3
Data Collection Design	4
Methods.....	4
Likely impact	5

ABSTRACT

There is considerable debate about the effectiveness of spine fusion surgery for degenerative disc disease (DDD) and other diagnoses related to chronic back pain. As many as 1-in-3 patients who undergo spine fusion do not report improvements in pain or functional status. Additionally, there are currently no evidence-based selection criteria to help surgeons determine which patients will respond to spine fusion surgery and which will not benefit.

The goal of this study was to better understand which patients are more likely to benefit from spinal fusion surgery. The Comparative Effectiveness Research Translation Network (CERTAIN) Spine Fusion Study partnered with spine surgery clinics to invite patients to participate in research activities designed to identify the impact of spine fusion surgery on the outcomes that matter most to patients. As part of this study, patients took surveys before and after their spine fusion surgery, and shared elements of their medical records for review. CERTAIN anticipated that this study would produce a paradigm that clinicians can use with patients to determine whether spine fusion surgery is right for them and identify any modifiable risk factors that may impact their response to surgery.

OBJECTIVE

Determine patient characteristics associated with non-response among patients undergoing lumbar fusion for DDD.

Rationale: *A patient's sense of activation in managing their health, loci of control, tendency towards catastrophizing, social support, satisfaction with work, self-perceived quality of life, expectations, general mental health, anxiety and depression, and extent of critical medication (e.g., opioids, sleeping aids) use have been associated with clinical outcomes and self-perception of health status. These parameters have not been well studied among those who fail to improve with spine surgery compared to responders. Nearly all Spine SCOAP patients undergo baseline and follow up surveys of patient reported measures. We will perform a prospective cohort study adding standardized measures of personality traits and mental health and will evaluate their association with changes in function and pain at six months after surgery.*

DESIGN

Recruitment Workflow Notes

All site specific processes are in *italics*

UWMC and HMC:

- *Patients were identified from surgery schedules* (eligible if: lumbar fusion (L1-S1), over 18, English as primary language, not revision surgery, surgery date in > 10 days (not official study inclusion criteria, but needed to ensure enough time for mailers))
- *Research staff screened each patients EMR to confirm eligibility and noted in EMR disclosure log*

- Research staff sent each eligible patient a recruitment mailer containing: consent form (2), HIPAA Authorization Form (2), Study Intro Letter, Baseline survey, and a return envelope
- One week after mailer was sent, phone recruitment began; 5 calls over ~10 days
- During phone call: research staff delivered screening questions, reviewed forms, outlined which were copies for patient's own records and which to return, gave instructions on how to return
- Patient was enrolled when consent and baseline were returned via mail (HIPAA form return did not impact enrollment)

Proliance:

- Patients were identified from an automated feed delivered from Proliance IT via secure email once a week* (eligible if: lumbar fusion (L1-S1), over 18, English as primary language, not revision surgery, surgery date in > 10 days (not official study inclusion criteria, but needed to ensure enough time for mailers))
- *Research staff screened schedule for potentially eligible procedures and noted in EMR disclosure log, even though Proliance EMR was not accessed at this time*
- Research staff sent each eligible patient a recruitment mailer containing: consent form (2), HIPAA Authorization Form (2), Study Intro Letter, Baseline survey, and a return envelope
- One week after mailer was sent, phone recruitment began; 5 calls over ~10 days
- During phone call: research staff delivered screening questions, reviewed forms, outlined which were copies for patient's own records and which to return, gave instructions on how to return
- Patient was enrolled when consent and baseline were returned via mail (HIPAA form return did not impact enrollment)

Evergreen Health:

- *Patients were identified by clinic staff* (eligible if: lumbar fusion (L1-S1), over 18, English as primary language, not revision surgery, surgery date in > 10 days (not official study inclusion criteria, but needed to ensure enough time for mailers))
- *Clinic staff screened and consented each patient in-person, and completed screening survey in Microsoft Forms to alert UW staff afterward*
- *If patient needed further outreach, UW research staff did phone outreach to complete forms, and sent recruitment mailer if needed* Mailer containing: consent form (2), HIPAA Authorization Form (2), Study Intro Letter, Baseline survey, and a return envelope
- One week after mailer was sent, phone recruitment began; 5 calls over ~10 days *if needed*
- During phone call: research staff delivered screening questions, reviewed forms, outlined which were copies for patient's own records and which to return, gave instructions on how to return *if needed*
- Patient was enrolled when consent and baseline were returned *from Evergreen; or via mail from patient directly* (HIPAA form return did not impact enrollment)

Original Recruitment Design

As designed in the original grant, Spine Fusion study was intended to be a research study built on top of a QI initiative (CERTAIN). The original plan was to tack the SF screening, consent, and if time allowed, baseline on to the end of the CERTAIN baseline that was implemented in several clinics at the time of

study start. This was meant to result in a nearly seamless process of QI data collection and study enrollment for eligible patients. Unfortunately, the implementation of CERTAIN did not allow for this workflow to come to fruition successfully.

Barriers:

- Tablets: Original grant depended on patients completing CERTAIN baseline for themselves via tablet in clinic waiting room, however, patients and staff had technical difficulty with tablets
- Time: not enough time in waiting room or during rooming process to complete the CERTAIN baseline, let alone SF screening and recruitment
- Variability: each CERTAIN clinical site implemented CERTAIN at a slightly different point in their workflow (i.e. in waiting room, after rooming, after surgery scheduling, etc.) which made it difficult to provide clinic staff with guidance about how to assist with enrollment
- QI vs. Research: by not classifying SF as a multi-site study with "engaged" sites, the flexibility to allow clinic staff to actively enroll patients was lost (the exception to this is Evergreen, who had separate IRB approval for a research-only approach to enrollment, not QI)

Data Collection Design

A combination of Quality Improvement (QI) databases and research databases were used to complete the final dataset for this study. Most hospitals in Washington (WA) State participate in a novel, prospective care surveillance initiative called Spine Surgical Care and Outcomes Assessment Program (Spine SCOAP) that allows benchmarking on the indications for, processes of care, clinical outcomes and changes in patient reported outcomes (PROs) including pain and function for patients undergoing spine surgery. Spine SCOAP's analytic group, the Comparative Effectiveness Research Translation Network (CERTAIN) assesses PROs at 60-90 days, 12 and 24 months. Spine SCOAP data was obtained through CERTAIN, and research data was collected directly from patients via email or mail, rather than in the clinic as originally proposed. These surveys included additional baseline, 60-day, and 1-year characteristics and the outcome measures to the original CERTAIN surveys through the DatStat platform.

Socio-demographic, clinical and procedural characteristics were collected from both Spine SCOAP, the CERTAIN QI surveys, and the additional research measures. Spine SCOAP data included age, zip code, race and ethnicity, insurance type, and employment status. Clinical characteristics included diagnosis and indication for surgery, preoperative comorbid conditions, known preoperative risk factors (e.g. cigarette smoking), laboratory results (e.g., albumin and HbA1c), and current medical treatments (i.e., statin, beta blocker, ACE or ARB inhibitors, therapeutic anticoagulants, steroids, and narcotic pain medication). Surgical approach (i.e. minimally invasive or open and anterior or posterior), perioperative care, fusion technique, instrumentation used and adverse clinical outcomes were also included.

METHODS

Ten CERTAIN clinics agreed to participate in the study, including: Confluence Health, Evergreen Health, Harborview Medical Center (HMC), UW Medical Center (UWMC), and six clinics from Proliance Surgeons. Within these CERTAIN clinics 28 surgeons participated. The sites represented close to 70% of

the Washington SCOAP network, with representation across public, private, and geographic healthcare settings.

INCLUSION CRITERIA:

Patients may enroll in Spine Fusion if they:

- Are receiving care from a spine surgeon at a participating clinic
- Are over 18
- Are fluent in English (able to take surveys via mail, phone, or online)
- Have lower back pain (pain for more than three months, or pain for at least half the days in the past 6 months)
- Are planning to have lumbar spine fusion surgery
- Have no history of previous spine surgery
- Are not a member of a vulnerable population
- Are able and willing to provide informed consent to participate in a research study

EXCLUSION CRITERIA:

Patients may not enroll in Spine Fusion if they:

- Are under 18 years of age
- Do not speak English (are unable to take surveys via mail, phone, or online)
- Do not have lower back pain (pain for less than three months, or not even for half the days in the last six months)
- Are not planning to have lumbar spine fusion surgery
- Have had spine surgery previously
- Are a member of a vulnerable population
- Indicate that they are unable or unwilling to provide informed consent to participate in a research study

For more information regarding the scientific background and statistical methods, see the Statistical Analysis Plan (SAP).

LIKELY IMPACT

This exploratory study is being conducted because the prevalence of these characteristics needs to be determined in order to develop accurate predictive algorithms and risk factors for non-response to lumbar spine fusion surgery. Additionally, the findings of this study will be used to establish a statistical and methodological framework to identify patients at high-risk for non-response, informing both decision makers and future interventions aimed at modifiable factors.

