STATISTICAL ANALYSIS PLAN

Study name	Understanding Non-Response in Spine Fusion Surgery
Principal investigators	[name], MPH
Project lead	[name], MPH
Document Date	2/6/2019
Team conducting analysis	[name], MS [name], MPH
Version	3

AIM 1

We will assess baseline covariates with respect to the primary outcome, the Oswestry Disability Index (ODI) failure to achieve at least a 15% improvement (minimal important clinical difference as established by the Food and Drug Administration [FDA]) in the ODI score which ranges from 0 to 100 where 0 indicates not disability and 100 indicates complete disability when comparing baseline to six months after surgical procedure, reporting proportions for categorical variables and means and other measures of central tendency for continuous variables. We will use a multivariate logistic regression model with robust standard errors to evaluate these covariates and the primary outcome. A latent class analysis will be used to identify clusters of traits (e.g., patients with depression, anxiety, and catastrophizing) that tend to be grouped together within patient subtypes. This technique assumes there are distinct patterns and that individuals can be grouped into a small number of clusters representing each outcome path (the “latent classes”). The association between clusters and non-response will be described using logistic regression models accounting for repeated testing. As a sensitivity analysis, we will repeat the latent class analysis on the raw percentage change of the primary outcome measure to examine the robustness of variables that define latent classes. We will also conduct a sensitivity analysis looking for different degrees of change in the primary outcome beyond the 15% threshold defined by the FDA. We will also conduct a missing data analysis to describe and characterize enrolled participants who do not provide further outcome measures due to attrition. We will conduct sensitivity analyses using 10-fold multiple imputation to assess the robustness of the results. We will create an imputation model with variables found to be predictive of missingness and data will be imputed to create 10 complete data sets. The results will then be combined across data sets with the using STATA (i.e., MI) statistical software packages.

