As a sensitivity analysis, we will repeat the latent class analysis on the raw percentage change of the primary outcome measure to examine the robustness of variables that define latent classes. We will also conduct a sensitivity analysis looking for different degrees of change in the primary outcome beyond the 15pts threshold defined by the FDA. We will also conduct a missing data analysis to describe and characterize enrolled participants who do not provide further outcome measures due to attrition. We

will conduct sensitivity analyses using 10-fold multiple imputation to assess the robustness of the results.

We will assess baseline covariates with respect to ODI non-improvement at 60 days, reporting proportions for categorical variables and means and other measures of central tendency for continuous variables. A multivariate logistic regression model with robust standard errors will be used to evaluate these covariates and the primary outcome: ODI non-Improvement at 60 days.

Use a latent class analysis to identify clusters of traits (e.g., patients with depression, anxiety, and catastrophizing) that tend to be grouped together within patient subtypes. This technique assumes there are distinct patterns and that individuals can be grouped into a small number of clusters representing each outcome path (the “latent classes”). The association between clusters and non-response will be described using logistic regression models accounting for repeated testing.

AIM 2

For responders and non-responders, we will perform a descriptive analysis of radiographic characteristics and compare proportions for categorical variables and means for continuous variables. We will explore the associations between radiographic measures and non-response using conditional logistic regression models, as appropriate for matched case-controls studies with multiple controls.

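### SAP Aim 1 has no rule for low baseline ODI: a 15-point threshold makes every patient below 15 a non-responder by construction, and a relative 15% threshold makes low scorers responders on trivial change

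*Protocol*

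**What the plan says.** **Entry.** The Protocol's Inclusion Criteria (Methods) contain one symptom requirement, "Have lower back pain (pain for more than three months, or pain for at least half the days in the past 6 months", and one surgical requirement, "Are planning to have lumbar spine fusion surgery". The site lists under Recruitment Workflow Notes ("eligible if: lumbar fusion (L1-S1), over 18, English as primary language, not revision surgery") add no disability level.

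**Outcome.** SAP Aim 1 describes "the ODI score which ranges from 0 to 100 where 0 indicates not disability and 100 indicates complete disability". Its primary outcome is "failure to achieve at least a 15% improvement", assessed "when comparing baseline to six months after surgical procedure". It does not say whether the percentage is of the patient's baseline or of the scale. Later in Aim 1 the same FDA threshold appears in points, in a planned sensitivity analysis of "different degrees of change in the primary outcome beyond the 15pts threshold defined by the FDA". The other degrees of change are not listed. Aim 1 also includes a 60-day non-improvement analysis with no threshold stated.

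**Low baselines.** Aim 1 gives no rule for a patient whose baseline is too low to reach the threshold, and does not name baseline ODI as an adjustment covariate. Neither document gives a baseline ODI distribution.

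**The concern.** Improvement on a scale with a floor of 0 cannot exceed the starting score. With no lower limit on baseline, at entry or in the analysis, a fixed threshold does not mean the same thing for every patient. For low scorers the label then reflects where they started more than what surgery did.

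The label is used throughout. It is the dependent variable in the Aim 1 logistic models and in the models linking latent classes to non-response, and Aim 2 compares responders with non-responders. The Protocol's objective is to find characteristics associated with non-response, and Likely Impact looks ahead to predictive algorithms and modifiable factors. Any trait that is rarer or commoner among patients with little disability could appear associated with non-response for a purely arithmetical reason.

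**Working it through.** The plan states no figure on this point, so there is none to reproduce. Steps 1 and 2 are arithmetic on the scale. Steps 3 to 5 rest on assumed inputs.

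**1. What each reading demands.** Let B be baseline ODI. The largest possible improvement is B. A 15-point rule can be met only if B ≥ 15, and requires a proportional reduction of 15/B. A relative 15% rule requires 0.15 × B points.

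| Baseline B | Largest possible gain | 15-point rule: reduction needed | Relative 15% rule: points needed |
|---|---|---|---|
| 5 | 5 | cannot be met | 0.75 |
| 10 | 10 | cannot be met | 1.5 |
| 14 | 14 | cannot be met | 2.1 |
| 15 | 15 | 100% | 2.25 |
| 20 | 20 | 75% | 3 |
| 30 | 30 | 50% | 4.5 |
| 60 | 60 | 25% | 9 |

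If 15% means 15% of the 0-100 scale, it equals 15 points and the third column applies. On the relative reading only B = 0 is blocked, and there percentage change is undefined.

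**2. Larger point thresholds.** A threshold of T points makes everyone with B < T a certain non-responder, so any T above 15 enlarges the group.

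**3. Share below 15 (assumed).** For a normal distribution with mean m and SD s, truncated to 0-100:

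P(B < 15) = [Φ((15−m)/s) − Φ(−m/s)] / [Φ((100−m)/s) − Φ(−m/s)]

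Example, m = 40 and s = 15: (0.0478 − 0.0038) / (1.0000 − 0.0038) ≈ 0.044.

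| Assumed mean | SD 12 | SD 15 | SD 18 |
|---|---|---|---|
| 30 | 10.0% | 13.9% | 16.2% |
| 40 | 1.8% | 4.4% | 7.0% |
| 50 | 0.2% | 0.9% | 2.3% |

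With T = 20 as an illustration (not a value in the plan), the mean 40, SD 15 share rises from 4.4% to 8.8%.

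**4. Effect on a trait odds ratio, points reading only (assumed).** Let a share f have B < 15 and be certain non-responders. Let 30% of the others be non-responders. Let a trait be present in 10% of the low group and 30% of the others, with no association with response among the others.

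- Non-responders: f + (1−f) × 0.30. Of these, f × 0.10 + (1−f) × 0.30 × 0.30 carry the trait.
- Responders: 30% carry the trait, odds 0.30/0.70 = 0.4286.
- At f = 0.06: non-responders 0.342, with trait 0.0906, without 0.2514. Odds 0.0906/0.2514 = 0.3604. Odds ratio 0.3604/0.4286 = 0.84.
- The same steps give 0.91 at f = 0.03 and 0.76 at f = 0.10.

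**5. Chance of response with no true change, relative reading (assumed).** Take normal error in the change with SD 5 to 10 and scores in 2-point steps. At B = 10 a drop of one step (2 points) is enough, so the error must be below −1: Φ(−1/5) = 0.42 to Φ(−1/10) = 0.46. At B = 60 a drop of 10 is needed, so the error must be below −9: Φ(−9/5) = 0.04 to Φ(−9/10) = 0.18. Noise alone makes low scorers responders far more often than high scorers.

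**The case against.** **The floor may not matter.** The primary outcome sentence says 15%; points appear only in a sensitivity-analysis sentence. Read as relative change, 15% is within reach at every baseline above 0. This stands. A reader might infer that the floor misclassifies low scorers whichever definition applies, but on the relative reading the error comes from trivial change and runs toward response.

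**Very low scores may be rare.** Entry already requires persistent back pain and a planned fusion. This is plausible, but the documents give no data either way.

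**The group is large among non-responders.** A reader might divide the step 3 shares by the Protocol Abstract's figure of up to 1 in 3 and get about 0.5% (0.0018 × 3) to 49% (0.1623 × 3) of all non-responders. The documents do not support that. The figure concerns no reported improvement in pain or function, not failure to gain 15 ODI points, so it is not the right denominator.

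**Adjustment for baseline could deal with it.** It is tempting to say that it could not. That is too strong: in step 4, stratifying at 15 returns an odds ratio of 1.00 among those who can respond. A linear baseline term helps only partly: with assumed mean 40 and SD 16 the odds ratio moves from 0.86 to just under 0.89. Either way, the plan names no such adjustment.

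**It is a choice of population.** A patient with too little disability to gain an important amount may fairly be counted as not benefiting, and removing such patients could hide a real predictor. This stands against changing the primary population. It does not stand against showing whether the associations depend on them.

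**Sensitivity analyses already exist.** Larger point thresholds enlarge the unreachable group. The percentage-change analysis repeats only the latent class analysis. Neither isolates the patients who cannot reach the threshold.

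**Conclusion.** The gap is real and belongs to SAP Aim 1. On the points reading, or 15% of the scale, a stated rule labels full recovery from any baseline below 15 as non-response; that is arithmetic and needs no assumption. On the relative reading the floor decides only baseline 0, and the weakness is response on trivial change. Settling 15% against 15 points therefore decides the direction of the problem but does not remove it.

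The size cannot be established from the documents. The 0.2% to 16% range rests on an assumed truncated-normal baseline with mean 30-50 and SD 12-18, and is sensitive to both. The odds ratios of 0.91 to 0.76 also rest on assumed trait prevalences and apply to the points reading only. If baseline scores are high, the effect is small.

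A reader might also infer that the pain criterion is faulty or that an ODI minimum was needed at entry. The documents do not support either: the criterion is coherent as written, and the problem can be handled in the analysis.

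**What to change.** In SAP Aim 1:

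1. Reconcile the 15% and 15-point wording into one definition. If a percentage is kept, say whether it is of baseline or of the scale, and how baseline 0 is coded.
2. Report the baseline ODI distribution, the number of patients whose baseline is below each threshold in points, and their follow-up ODI.
3. Pre-specify a sensitivity analysis that repeats each responder logistic model and each latent-class association model without those patients, shown beside the full-cohort result. The limit is baseline below 15 for the primary threshold and the matching value for each larger point threshold. If the relative definition is kept, use 15 as well. It is then a convention, since nothing changes at that value (2.1 points needed at 14, 2.25 at 15).

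The paired display matters because the excluded group changes with the threshold. Excluding patients below 15 removes only the impossible cases: baseline 20 still needs a 75% reduction on the points rule.

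Cost: SAP wording, one extra run on data already collected, and slightly fewer patients in the sensitivity models. Recruitment, data collection and the primary population stay as they are.
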